Document type: Statistical Analysis Plan

Study title: Development and Pilot Test of an mHealth Interactive Education and Social Support Intervention for Improving Postnatal Health – Phase 2

NCT number: NCT04693585

Document date: April 1, 2020

STATISTICAL DESIGN AND POWER

The proposed research includes two separate research phases to achieve our research aims: 1) To develop optimal intervention functions and mHealth technology delivery platforms for education and peer support among postnatal women in rural India; and to pilot test the optimized intervention and assess 2) feasibility and acceptability, and 3) preliminary effectiveness on maternal and infant health outcomes. Due to the exploratory nature of these aims, the sample sizes for our two study phases have been designed for feasibility, not for adequate power for statistical testing. After completing the study activities proposed herein, we plan to robustly test the effectiveness of our mobile educational and social support intervention through a larger multi-site R01 study.

Phase 1 (Aim 1). As described within our research strategy, the developmental phase 1 will employ a prototype platform will assess women's preferences for intervention functions, processes and platforms in order to design the most appropriate intervention for full piloting. Data collection during this phase includes capture of back-end data for participation and content, and survey (all participants) and in-depth interview (subset of participants) to understand preferences.

- Backend data: intervention participation, intervention engagement, content of group discussions, content of text messaging.
- Survey: Preferences regarding group components, functions and modalities.
- In-depth interview: Preferences regarding group components, functions and modalities.

Quantitative data will be analyzed for means and proportions using STATA version 15. Text data from discussion/messaging and in-depth interviews will be analyzed for content and themes using Atlas.ti software.

Phase 2 (Aims 2 & 3). Our pilot test of the optimized intervention functions, processes and platforms will use a four-arm controlled factorial between-groups design:

MeSSSSage components to be tested in Phase 2.	Arm 1	Arm 2	Arm 3	Control
Real-time live voice call group meeting: Interactive educational program with scripted didactic component plus discussion/question. Lead and moderated by health professional. (voice)	X		X	
Text-based, asynchronous, on-demand social support: App-based small group text-based communication. Moderated by health professional. (text)		X	X	
Standard of care: 3 visits in the first 7 days postnatal (facility and home)	X	X	X	X

The following intervention characteristics will be assessed:

Feasibility. To evaluate feasibility of the intervention, we will monitor enrollment rates and moderator effort required (e.g. number of staff hours). An enrollment rate of 70% or higher will be considered feasible, as the established standard in intervention literature. Through moderator report we will confirm effort required for preparation, session delivery, and follow-up. We will also capture any technological challenges. This information will inform staffing needs and retention protocols for a subsequent full trial.

Acceptability. To measure acceptability, we will use a client satisfaction questionnaire which will capture self-reported engagement in intervention components and topics, satisfaction with intervention components, likelihood of participating again, likelihood of recommending program, and value on knowledge and social support gained from participation.

Preliminary effectiveness. To measure effectiveness, we will health-related knowledge (maternal and neonatal danger signs, best practices for infant care, and family planning), health-related behaviors (breastfeeding and complementary food introduction practices (breastfeeding initiation, length of exclusive breastfeeding, length of breastfeeding, timing of complementary food introduction), appropriate management of early childhood

illnesses), and health outcomes (Early childhood immunization, postnatal depression and anxiety, postnatal contraceptive adoption.)

Quantitative analyses: With a between-groups design, each participant will participate in only one arm of the trial, thus we will assess quantitative intervention outcomes by factor (voice and text) through fitting a series of the following linear regression model:

$$y_i = \beta_0 + \beta_1 Z_{1i} + \beta_2 Z_{2i} + \beta_3 Z_{1i}Z_{2i} + \varepsilon_i$$

Where y_i is the outcome for the i^{th} participant, β_0 is the coefficient for the intercept (standard of care), β_1 represents the mean difference in factor 1 (voice), β_2 represents the mean difference in factor 2, (text) β_3 represents the interaction between factor 1 and factor 2 (voice + text), Z_{1i} is the indicator variable for factor 1, Z_{2i} is the indicator variable for factor 2, and ε_i is the residual for the i^{th} participant. Due to the modest sample size, significance testing will be deemphasized and we have not included power analyses for this study.

Hypotheses for preliminary/exploratory analyses on effectiveness. Exploratory hypotheses will be evaluated as part of the study feasibility assessment process. Means and proportions will be plotted by group over time to enable descriptive evaluation of overall patterns of change across time in the outcomes for the intervention and control groups. For example, we expect that following intervention exposure, relative to control group participants, intervention participants will have improved health-related knowledge, health-related behavior, and health outcomes. We also anticipate that intervention participants receiving both voice and text components will have the highest report of the prior outcomes and reported social support, and we will explore differences in these outcomes and in levels of reported social support between the groups as described above.

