Document type: Study Protocol

Study title: Development and Pilot Test of an mHealth Interactive Education and Social Support Intervention for Improving Postnatal Health – Phase 2

NCT number: NCT04693585

Document date: April 1, 2020

Specific Aims: We propose developing a mobile interactive education and support group intervention, *Maa Shishu Swasthya Sahayak Samooh (MeSSSSage)*, to improve the health and well-being of Indian women and infants in the postnatal period using a provider-moderated group approach. *MeSSSSage* will provide culturally tailored educational programming, increase women's health-related communication with providers, refer women in a timely and appropriate manner, and connect them with a virtual social support group of other new mothers. *MeSSSSage* aims to reduce postnatal care barriers arising from distance, economic burden, cultural practices, and fatigue, and provide social support in this time to help reduce women's postpartum isolation.

Postnatal health care includes education and clinical care necessary for ensuring maternal and infant health: neonatal care practices (breastfeeding, newborn hygiene, etc.), prevention activities (immunization, recognition of infant danger signs, etc.), assessment of maternal physical recovery from childbirth, postpartum mental health, and postnatal contraception adoption. Postnatal care improves maternal physical and mental health, and well-being.¹⁻³ In Haryana state, India, only 40% of women received at least one postnatal health check in the two months after delivery.⁴ Extending group-based pregnancy care or women's group models that have proven successful in improving maternal and neonatal outcomes in South Asia and elsewhere to the postnatal period could show health improvements.² However, barriers exist to successfully implement postpartum group care, including logistical challenges of traveling to the facility or group meeting with a young baby and limited mobility in South Asia, including postnatal seclusion.⁶ Applying an mHealth approach to postnatal care may help new mothers overcome such challenges, and high mobile phone penetration in Haryana state, India, supports the feasibility of testing a group mHealth intervention in this population.

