Aim 2. To assess the feasibility and acceptability of the optimized *MeSSSSage* intervention. In Phase 2 we will evaluate the feasibility and acceptability of two intervention components using a controlled 4-arm factorial design (n=160; 40 per arm): 1) real-time mobile voice information and support group alone, 2) asynchronous/on-demand text-based group support only, and 3) real-time mobile voice information and support group plus asynchronous/on-demand text-based group support. Feasibility and acceptability will be assessed via back-end data, surveys, and IDIs with purposively selected participants (n=30) and moderators.

Aim 3. To explore the preliminary effectiveness of the optimized *MeSSSSage* intervention components on six-month maternal and neonatal health outcomes. Phase 2 data will help us develop a preliminary understanding of the impacts of the intervention components on MCH health-related knowledge, behaviors and outcomes including exclusive breastfeeding, immunization, family planning uptake, postnatal visits, mental health and empowerment; however, it is not statistically powered to formally assess effectiveness.

This study is significant and innovative in addressing key priorities of NICHD's Pregnancy and Perinatology Branch and using systematic, user-centered and experience-driven design approach. These results will inform the most acceptable, feasible, and potentially efficacious intervention design to be robustly tested through an R01 mechanism to assess effectiveness for maternal and infant health outcomes, explore other research questions relevant to intervention development and scale-up for postnatal health among South Asian women, and explore generalizability across populations.

Significance

[figure not shown]

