Women age 18 or above are eligible if this is their first birth. Women with high risk pregnancies will be ineligible for participation, and enrolled women will be removed from the study if they deliver preterm, suffer severe maternal complications (c-section or hospitalization), or they or their baby are otherwise sick in the first week postnatal. When women give birth, the ASHA and facilitator will inform the research team, and women will be assigned to groups based on date of delivery to cluster delivery dates in within approximately two weeks.

Back-end data will be captured from all participants. A brief phone survey with all participants and in-depth interviews with half of participants will be conducted after 2 months (~ 8 group meetings).

Surveys and backend data: All 48 respondents will be called via phone to participate in a short (10 min) survey about their experiences with MeSSSSage group components, including preferences regarding functions and modalities and level of satisfaction with each, using likert-type response scales (1-5). Data will be recorded on a tablet. We will calculate means and standard deviations for each preference and function variables. Each group discussion will be audio recorded, transcribed, and translated into English. We will analyze group discussion content for function, using Atlas.ti. We will review intervention engagement including text-messaging (number

and topic), number of participants per session, engagement with the health worker and each other, etc. The study team has previously analyzed prior technological study data; we will use a similar method, in STATA v15.

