Table 2: *MeSSSSage* components to be tested in feasibility and acceptability assessment (Phase 2).

	Arm 1	Arm 2	Arm 3	Control
Real-time live voice call group meeting: Interactive educational program with scripted didactic component plus discussion/question. Lead and moderated by health professional.	X		X	
Text-based, asynchronous, on-demand social support: App-based small group text-based communication. Moderated by health professional.		X	X	
Standard of care: 3 visits in the first 7 days postnatal (facility and home)	X	X	X	X

Procedures: Unless found not feasible or acceptable within Phase 1 activities, women will be recruited using the approach described above (Aim 1). At the time of enrollment, the study protocol will be described to the women per informed consent procedures. Written confirmation will be obtained from interested women and their phone numbers will be collected (and tested). Women without a phone will be provided with a phone and all participants' airtime will be covered for the length of the 6-month research project. Women who consent will be randomly enrolled into 1 of the 4 study arms using a random number generator. We will test each study condition using 2 groups of women, with intervention initiation staggered 1 month apart. Women in the control group will receive the standard of care. All women will be given 50 Indian Rupees for participation in each session (in addition to airtime and phone if needed), and ASHAs will receive 150 Indian Rupees for moderating each session. Assessment of feasibility and acceptability (Aim 2) and preliminary effectiveness (Aim 3) will be accomplished using mixed-methods including quantitative surveys, in-depth interviews, and technology assessment.

Survey data collection: Baseline and endline surveys will be administered by a research assistant in the respondent's home. Endline survey will be collected roughly 6 months postnatal, after potential participation in ~24 *MeSSSSage* sessions (details to be determined during Phase 1). We will capture women's health record cards and ASHA registers to validate self-reported health outcome data. Data will be collected on a tablet using the secure REDCap mobile research administration app, stored in a password protected database at UCSF, and no identifiable information will be included with analytic datasets (identifiable data will be stored separately).

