Sociodemographic characteristics	Age, age at marriage, educational attainment, caste, language spoken, household assets, women's status/decision-making, social support and relationship quality.
Health-related knowledge (effectiveness)	Knowledge on maternal and neonatal danger signs, best practices for infant care, family planning.
Health-related behaviors (effectiveness)	Breastfeeding and complementary food introduction practices (breastfeeding initiation, length of exclusive breastfeeding, length of breastfeeding, timing of complementary food introduction), appropriate management of early childhood illnesses.
Health outcomes (effectiveness)	Early childhood immunization, postnatal depression and anxiety, postnatal family planning adoption.
Intervention perspectives (feasibility, acceptability)	Self-reported engagement in intervention components and topics, satisfaction with intervention components, likelihood of participating again, likelihood of recommending program, value on knowledge and social support gained from participation.

Analysis. *Aim 2. Feasibility and acceptability of the optimized MeSSSSage intervention components.* We will use a mixed methods approach, triangulating data from quantitative baseline and endline data, qualitative IDIs, and technology assessment. Feasibility and acceptability will be measured by participation rates at each session, participation trajectories over time, and user engagement (via technology assessment backend data). Women's reports of use and satisfaction (survey and IDI will shed light on barriers and facilitators to participation. Moderator acceptability will be assessed by satisfaction, fidelity to topic/content based on protocol and perspectives on impact. We will test for differences in feasibility and acceptability between the three intervention arms to understand if both components (group meetings and text) or only one is the best approach, using ANOVA for continuous outcomes and chi-square or Fisher's exact tests, as appropriate, for categorical outcomes.

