15. Inclusion of Women and Minorities

All research participants for the proposed research will include women over the age of 18 who have recently delivered an infant (postpartum women). Research participants are limited to women due to the postnatal health focus of this research. Women will be recruited in the end of pregnancy, but the intervention will begin postpartum.

It is possible that some ethnic or religious minority groups will be part of the study population. According to the 2011 Census of India, the vast majority of the population in Haryana state is Hindu (87.5%), followed by Muslims (7.0%), and Sikhs (4.9%) as the largest minority groups. We will not include or preclude respondents based on their ethnic or religious status. All research activities will be conducted in the Hindi language, which is the prevalent language of this region.

16. Inclusion of Children

Individuals over the age of 18 will be eligible for study participation. The study sample will include women who recently gave birth (recruited at the end of pregnancy). We will collect data on birth weight, health seeking behaviors, and infant health outcomes. No infant will be over 6 months of age by the end of the study. If infant health problems are detected, infants will be referred to the local hospital for evaluation and treatment. We are working closely with health providers, both the community health workers and higher-level providers, and there are medical professionals (an OBGYN and a nurse midwife) on our research team. When an infant is identified as having any serious illness, he/she will be referred to the appropriate health facilities.

Worldwide, an estimated 3 million newborns die within the first month of life. Over 40% of the under-5 child mortality occurs during the neonatal period. The infant mortality rate in our study population is 22/1,000 live births. This study will follow infants during the neonatal period and may identify intervention approaches that would reduce rates of neonatal morbidity and mortality among a vulnerable group of infants.

RECRUITMENT AND RETENTION PLAN

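### Breastfeeding initiation is listed as an effectiveness outcome although it precedes the group intervention, so an arm difference in it cannot be read as an effect

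*SAP*

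**What the plan says.** **The outcome lists.** Under Preliminary effectiveness, the SAP names "breastfeeding initiation, length of exclusive breastfeeding, length of breastfeeding" among the health-related behaviours. The protocol has the same item in the Table 3 row marked as effectiveness and in the matching paragraph of Statistical Design and Power. The SAP then fits a linear factorial model (voice, text and their interaction) to the quantitative outcomes. It expects improvement after exposure, relative to control.

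**When exposure starts.** Protocol section 15 states: "Women will be recruited in the end of pregnancy, but the intervention will begin postpartum". The Phase 1 procedures add that, once they have given birth, "women will be assigned to groups based on date of delivery to cluster delivery dates in within approximately two weeks". They also remove women after enrollment for preterm delivery, severe maternal complications, or illness of mother or baby in the first week. The Phase 2 procedures reuse the Phase 1 recruitment approach unless it proves unworkable. No document gives a start day.

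**When initiation is asked.** Under Measures, the described baseline content has no feeding-practice item. Breastfeeding is in the endline survey, at roughly 6 months and after up to about 24 sessions.

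**Visits.** Specific Aim 3 lists "family planning uptake, postnatal visits, mental health and empowerment" among its outcomes and gives no window for the visits. Visits are absent from Table 3, from the main outcomes in the Aim 3 analysis text, and from the SAP list. Three visits in the first 7 days are standard of care in all four arms.

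**The concern.** An effectiveness outcome has to be able to respond to the intervention. Initiation happens at or just after birth, and the groups exist only afterwards, so the factorial model would be fitted to something already settled. The coefficients would still be estimated, and the Aim 3 analysis text calls for effect sizes against control. A difference in initiation could then be listed with the preliminary effectiveness results, which the protocol says will inform the design of a larger trial.

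The error need not be neutral. Women who have been taught about breastfeeding for months may recall or report its start more favourably than controls, which would tilt a spurious difference towards the intervention. Removal of women for events around birth, if it applies in Phase 2 and follows randomization, could also leave arms that differ on factors related to initiation.

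**Working it through.** **1. Sample size.** Specific Aim 2 gives 40 per arm in 4 arms: 4 × 40 = 160, which reproduces the stated total. The documents give no alpha, power or effect size to check.

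**2. Order of events for initiation.**

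| Event | Timing in the documents |
|---|---|
| Consent, enrollment, training in using the platform | Last month of pregnancy |
| Randomization | Described after consent; timing relative to birth not explicit |
| Birth, then breastfeeding initiation | Initiation not defined; taken here as the start of breastfeeding at or soon after birth |
| Group assignment from delivery dates | After birth (Phase 1 text) |
| Voice and text groups | Postpartum; no day stated |
| Breastfeeding questions | Endline, about 6 months |

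Initiation comes before the groups, and its measurement comes after them. The groups can therefore affect how initiation is reported, but not the initiation itself.

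**3. What the timing does not settle.** Six months is 6 × 30.4375 / 7 = 26.1 weeks. If sessions are weekly (an assumption taken from the Phase 1 prototype), 24 sessions span 23 weeks. Completing all of them by a 6-month endline puts the first no later than about week 26.1 − 23 = 3.1. If births in a group spread over 14 days and the group opens when the last-born infant is 7 days old (also an assumption), infants are 7 to 7 + 14 = 21 days old at the start. Both figures fit a start after the first week, but neither proves it.

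**4. Size of a chance difference.** In the indicator-coded model with interaction, β1 compares Arm 1 with control and β2 compares Arm 2 with control, each 40 against 40. With no true effect and a common initiation proportion p, the 95% range of the difference is ±1.96 × √(2p(1 − p)/40). The documents give no value of p, so a range is shown:

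- p = 0.9: 1.96 × √(0.18/40) = 1.96 × 0.0671 = 0.131, about ±13 points
- p = 0.7: 1.96 × √(0.42/40) = 1.96 × 0.1025 = 0.201, about ±20 points
- p = 0.5: 1.96 × √(0.50/40) = 1.96 × 0.1118 = 0.219, about ±22 points

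These figures assume that all 40 women per arm are analysed. Attrition widens them. They do not include bias from recall or removal, which is additional.

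**The case against.** The strongest reply is that little hangs on this. Initiation is one item inside a bracketed list. The main behaviour outcome is exclusive breastfeeding at 6 months, and the other main outcomes are knowledge, immunization and family planning uptake. The study is not powered for effectiveness, the SAP gives little weight to significance tests, and the chance range above would apply to any binary outcome at 40 per arm. All of this stands. It limits the importance of the point but does not make initiation able to respond to the groups.

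A second reply is that the post-delivery grouping and removal rules are Phase 1 text, that Phase 2 carries over only the recruitment approach, and that women may know their arm before birth. This stands in part. The main point, however, rests on the protocol's general statement that the intervention begins postpartum. The only earlier contact described is enrollment training in using the voice and text components, with no mention of feeding content.

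A reader might go further and infer that the first-week visits are themselves counted as effectiveness outcomes, or that all three standard visits are shown to precede exposure. The documents support neither. Postnatal visits appear as an outcome once, without a window, and the protocol's own background figure uses a longer one: "only 40% of women received at least one postnatal health check in the two months after delivery". Later visits can respond to the groups. A start after day 7 is plausible but not stated, and a text group opening in the first week is not excluded.

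**Conclusion.** The point holds for breastfeeding initiation. It is listed three times as an effectiveness behaviour, but the group intervention cannot change it. An arm difference would have three candidate explanations: chance (about ±13 to ±22 points over assumed rates of 90% to 50%), removal after enrollment, and differential recall at endline. A reader might stop at chance and selection. That is too narrow, because the outcome is asked after months of breastfeeding education.

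For postnatal visits the conclusion is weaker: the outcome is undefined, and any first-week visits counted in it would probably precede the groups.

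The conclusion assumes that initiation means the start of breastfeeding at or soon after birth, and that enrollment training carries no feeding content. The consequence is modest, given the exploratory aim and the separate main outcomes. The correction is still worth making because it is simple and prevents a misreading.

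**What to change.** **Initiation.** Remove it from the effectiveness list in protocol Table 3, in the Preliminary effectiveness paragraph of the protocol's Statistical Design and Power section, and in the same paragraph of the SAP. Add wording such as:

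> Breastfeeding initiation will be reported by arm as a negative-control variable. Because it precedes the group sessions, its coefficients in the factorial model will not be interpreted as intervention effects. If it is asked only at endline, it is subject to recall and attrition and is not a clean check of baseline comparability.

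This costs three wording changes and needs no new data.

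**Visits.** If postnatal visits are analysed, state when the groups start in each recruitment wave. Count visits after that date, and apply the same reference date to that wave's controls. Report any first-week visits descriptively. First confirm that the health cards, the ASHA registers or the survey record visit dates. The protocol plans to use cards and registers to validate self-reported health outcomes, but does not say that visit dates are extracted. If they are recorded, the cost is a definition and some data extraction; if not, a survey item would have to be added.

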Aim 3. Preliminary effectiveness of the MeSSSSage intervention components on six-month MCH outcomes. Using the quantitative survey data, we will statistically evaluate differences by study arm in improvements in women's knowledge, behaviors, and maternal and child health outcomes, compared to the control group (including effect sizes, controlling for relevant socio-demographics as necessary). Figure 1 displays the outcomes that are theoretically related to our intervention targets. Our main *knowledge* outcome will be a composite score representing the proportion of correct answers from a knowledge scale on breastfeeding, newborn and infant care, maternal and infant danger signs, newborn care, and family planning, topics that will be covered within our interactive educational group component. Our main *behavior* outcome will be self-reported exclusive breastfeeding at 6 months. Our main *health related* outcomes will be: (1) completion of early childhood immunization schedule; and (2) postnatal family planning uptake. We will measure women's social support and related mental health status (depression and anxiety) using scales that have been previously validated in similar populations such as the Hopkins Symptom Checklist⁴¹ and the Multidimensional Scale of Perceived Social Support⁴². Finally, women's empowerment will be measured using decision-making and mobility scales.^{43,44}

Sample Size. This pilot development study is not formally powered to detect significant differences in outcomes, but will give insight into directionality of changes. The per group sample size was selected based on feasibility

of recruitment, intervention delivery, and the interpersonal interaction important for a group-focused intervention. The sample is sufficiently large to assess the feasibility and acceptability outcomes through descriptive statistics.

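### Breastfeeding lengths and food timing are right-censored at the single endline survey, but the only model given is linear regression, and food timing has no value for women who delay food longest

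*SAP*

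**What the plan says.** - **Outcomes.** The SAP (Preliminary effectiveness) lists three durations among the health behaviours: length of exclusive breastfeeding, "length of breastfeeding, timing of complementary food introduction". The protocol (Table 3; Statistical Design and Power) has the same three: "length of exclusive breastfeeding, length of breastfeeding, timing of complementary food introduction".
- **Measurement.** Protocol, Survey data collection: "Baseline and endline surveys will be administered by a research assistant in the respondent's home". Recruitment is in the last month of pregnancy, so only the endline survey can capture these outcomes. Its timing is loose: "Endline survey will be collected roughly 6 months postnatal". The protocol's section on inclusion of children adds: "No infant will be over 6 months of age by the end of the study".
- **Analysis.** SAP, Quantitative analyses: "we will assess quantitative intervention outcomes by factor (voice and text) through fitting a series of the following linear regression model". The model has an intercept, voice, text and their interaction. The same text is in the protocol. It is the only effectiveness model written out.
- **Main behaviour outcome.** Protocol, Aim 3 analysis: "Our main *behavior* outcome will be self-reported exclusive breastfeeding at 6 months". This is a status, not a duration.

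Neither document mentions censoring, a restricted mean or a fixed age for the three durations. Neither gives a coding rule for women who have not reached the event by endline.

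**The concern.** A duration seen through one survey at about six months is right-censored for every woman who has not stopped, or not started, by then. A linear model needs a number for each woman, and the plan does not say which.

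For the two breastfeeding lengths, infant age at interview can be entered as the length so far. For food timing there is no natural entry. A woman who meets the main behaviour outcome and is still exclusively breastfeeding at interview has, by definition, not introduced food. Unless a rule assigns her a value, she leaves the regression. What remains is a comparison among early introducers, selected on the outcome itself. If the intervention delays food, more women leave from its arms, and part of the benefit leaves with them.

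The protocol offers direction of change and effect sizes as products of the pilot, to inform a larger trial. Putting less weight on significance tests does not repair a contrast computed in a selected subset.

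**Working it through.** The documents give no effect, event or power figure for these outcomes, so there is no stated figure to reproduce.

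**Step 1. Share without a completed value.** Inputs: 160 women, 40 per arm (protocol, Aim 2); exclusive breastfeeding 50.3% in Haryana (protocol, Significance; infant age not given). If that rate holds at survey age:
- 0.503 × 160 = 80.5 women, or 0.503 × 40 = 20.1 per arm, have neither an end of exclusive breastfeeding nor a food-timing value.
- Exclusive breastfeeding implies breastfeeding, so 80.5 is a lower bound for women without a completed breastfeeding length.
- Over an assumed range of 30% to 95% not yet at the event, 12 to 38 of 40 women per arm have no completed value.

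**Step 2. Effect of keeping only completed values.** Assumptions, none from the documents: exponential times, event-free share S in control at 26 weeks, hazard ratio 0.67.
- Control rate: λ = −ln(S)/26. Intervention rate: 0.67λ.
- Restricted mean to t: (1 − e^(−λt))/λ.
- Mean among events by t: 1/λ − t·e^(−λt)/(1 − e^(−λt)).

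At S = 0.503, λ = 0.02643 and 0.67λ = 0.01771 per week.
- Restricted mean to 24 weeks: 19.55 − 17.77 = 1.78 weeks.
- Mean among events by 26 weeks: 12.01 − 11.52 = 0.48 week (before rounding).
- Women left per 40: control 40 × 0.497 = 19.9; intervention 40 × (1 − 0.631) = 14.8.

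With both measures at 26 weeks the figures are 2.03 and 0.48, so the shrinkage does not come from the different horizons.

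| S at 26 weeks | Restricted-mean gain to 24 weeks | Difference among completed values | Women left per 40, control / intervention |
|---|---|---|---|
| 0.30 | 2.44 | 0.82 | 28.0 / 22.1 |
| 0.503 | 1.78 | 0.48 | 19.9 / 14.8 |
| 0.70 | 1.09 | 0.25 | 12.0 / 8.5 |
| 0.95 | 0.18 | 0.04 | 2.0 / 1.4 |

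**Step 3. Entering age at interview instead (the two breastfeeding lengths).** Take interviews spread uniformly over 24 to 26 weeks, alike in all arms. Linear regression on the recorded length then estimates the restricted mean averaged over those ages. It gives 1.91 weeks at S = 0.503 and 0.20 week at S = 0.95, against 1.78 and 0.18 for the restricted mean to 24 weeks. The two nearly agree.

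**Step 4. Differing interview ages.** With no true effect, mean interview ages of 27 and 26 weeks create a difference of (e^(−26λ) − e^(−27λ))/λ = 0.50 week at S = 0.503. By chance alone such a gap is unlikely: for independent ages uniform over 24 to 28 weeks, the standard error of the arm difference is √[(4²/12) × (2/40)] = 0.26 week, so one week is 3.9 standard errors.

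**The case against.** The strongest reply is that linear regression on a duration cut at one common age is a legitimate restricted-mean contrast. That stands for the two breastfeeding lengths if interview ages are similar across arms, as step 3 shows, and the six-month limit on infant age narrows the spread. It does not rescue food timing, where a woman who has not begun has no value to cut.

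A reader might infer that the breastfeeding-length contrasts chiefly reflect interview dates. The documents do not support this. Women are individually randomised, and each recruitment month fills one group per arm. Varying interview ages add noise, and bias arises only if arms differ systematically. One point stays open: there are two groups per arm, and the documents do not say whether endline visits are scheduled by group. If they are, an assumed between-group standard deviation of 0.5 to 1 week gives an arm-difference standard deviation of √(0.5² + 0.26²) = 0.56 to √(1² + 0.26²) = 1.03 weeks. That is still noise, but more of it.

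A reader might also infer that most women lack a completed value. The documents' one figure supports about half for exclusive breastfeeding and food timing, and at least half for any breastfeeding, and only if it applies at survey age.

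It is also fair that the questionnaire is not in the documents, so dropping women without a food timing is the consequence of the stated model on recorded values, not a stated rule. Finally, no decision rule rests on these outcomes.

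**Conclusion.** The point holds in a limited form. Three listed effectiveness outcomes are right-censored at one endline survey, the only model given takes no account of that, and no coding rule fills the gap. For food timing, regression on recorded values conditions on the outcome and excludes women who delayed longest. In the illustration this cuts a gain of about 1.8 weeks to about 0.5 week and leaves about 20 control and 15 intervention women of 40. Those sizes rest on assumed exponential times, an assumed hazard ratio of 0.67, and the 50.3% figure applying at 26 weeks. For the two breastfeeding lengths the fault is smaller: an unstated estimand and a cut-off that varies between women.

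Severity is low to moderate. The main behaviour outcome is a status and is unaffected, and these are exploratory outcomes of an unpowered pilot.

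**What to change.** For these three outcomes, replace the linear model in the SAP as follows.

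- Name one common infant age that all endline interviews will reach, and state how it relates to the 6-month main behaviour outcome.
- Give Kaplan-Meier curves by arm and restricted mean time to that age, censoring women without the event at infant age at interview.
- Report the SAP's contrasts on that scale: voice minus control, text minus control, and interaction = both − voice − text + control.
- Alternatively, report the proportion event-free at that age: still exclusive, still breastfeeding, no other food yet.

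If every interview does reach the common age, the restricted mean is simply the average of the smaller of event time and that age. Women who have not introduced food then count at the common age instead of being lost.

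Cost: SAP wording and standard code. The sponsor should confirm that delivery and interview dates are both kept. Delivery dates are used to form groups, but the documents do not expressly list infant age at interview as recorded.
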